5. RATIONALE AND BACKGROUND

Renal cell carcinoma (RCC) is the most common kidney cancer, accounting for about 90% of all kidney cancers. ¹⁻³ It accounts for 2-3% of all adult malignancies with an estimated 63,000 incident cases and 14,000 deaths per annum in the United States. ⁴ Approximately 25-30% of patients with RCC are diagnosed with metastatic disease due to the lack of early symptoms and clinical indications of disease. ⁵ Prognosis is poor among metastatic renal cell carcinoma (mRCC) patients, with 5-year survival rates of 5-10%. ⁶ As the population ages and risk factors for RCC become more prevalent, the burden of mRCC is expected to grow. ¹⁻³

Among patients with relapse or stage IV and surgically unresectable RCC, the National Comprehensive Cancer Network (NCCN) recommends sunitinib and pazopanib as category 1, preferred first-line targeted therapy treatments. More recently, NCCN expanded its first-line RCC treatment recommendations to include cabozantinib after the Food and Drug Administration (FDA) approved cabozantinib for first-line treatment of mRCC in December 2017 based on the CABOSUN (NCT01835158) trial results. The CABOSUN trial was a randomized, open-label phase II multicenter study in 157 patients with intermediate and poor-risk previously untreated clear cell mRCC. Intermediate and poor risk were classified based on IMDC prognostic risk groups (favorable, intermediate and poor). Patients received cabozantanib (n=79) 60 mg orally daily or sunitinib (n=78) 50 mg orally daily (4 weeks on treatment followed by 2 weeks off) until disease progression or unacceptable toxicity.8 Estimated median progression-free survival (PFS) for patients taking cabozantanib was 8.2 months (95% confidence interval [CI]: 6.2, 8.8) compared with 5.6 months (95% CI: 3.4, 8.1) for patients taking sunitinib (hazard ratio for progression or death = 0.66; 95% CI: 0.46, 0.95; p=0.012). Based on these results, the NCCN guidelines recommended cabozantinib for first-line RCC treatment in poor- and intermediate-risk groups.

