Findings from the CABOSUN trial showed that patients (IMDC intermediate and poor risk) taking sunitinib had a PFS of 5.6 months. This was lower than the results from a phase III trial that examined sunitinib versus interferon alfa in untreated clear cell mRCC patients where the PFS was 11.0 months in the sunitinib group vs. 5.0 months in the interferon alfa group. A recent retrospective analysis of the phase III trial demonstrated that, of the 373 patients treated with sunitinib, there were 36% favorable, 55% intermediate, and 9% poor based on the IMDC prognostic risk group. In addition, the median PFS for patients treated with sunitinib was 14.1 months (95% CI: 13.4, 17.1), 10.7 months (95% CI: 10.5, 12.5), and 2.4 months (95% CI: 1.1, 4.7) for favorable, intermediate, and poor risk groups, respectively. When intermediate and poor IMDC risk groups were combined. the median PFS was 10.6 months (95% CI: 8.1, 10.9). 10 CheckMate 214 was another phase III trial that compared nivolumab plus ipilimumab (nivo+ipi) with sunitinib for previously untreated clear cell mRCC. The results from this trial showed that among patients in the intermediate and poor IMDC risk groups, the median PFS was 11.6 months (95% CI: 8.7, 15.5) in the nivo+ipi vs. 8.4 months (95% CI: 7.0, 10.8) in the sunitinib. Of the 426 patients in the intermediate and poor risk groups, 334 (79%) and 91 (21%) patients were identified as intermediate and poor risk, respectively. 11 Based on the differences in PFS between these studies, patient IMDC prognostic risk group may play a role in the effect of first-line treatment on clinical outcomes.

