In addition to differences between IMDC prognostic risk groups, heterogeneity may exist within a risk group as well. Specifically, patients with IMDC intermediate risk group (defined as having 1 or 2 IMDC risk factors) may have different clinical outcomes depending on the number of risk factors. A retrospective analysis of six clinical trials examining sunitinib treatment for mRCC reported that among patients in the intermediate risk group, time interval less than 1 year from RCC diagnosis to targeted therapy was the most common risk factor as observed in 36% of patients with 1 risk factor alone or in combination with low serum hemoglobin as observed in 25% of patients with 2 risk factors. The study also found that patients with 1 risk factor had longer OS (25.6 vs. 16.3 months) and PFS (9.8 vs. 8.6 months), and greater ORR (39.5% vs. 31.8%) when compared to those with 2 risk factors. 12 These results are comparable to those from the retrospective analysis of sunitinib vs. interferon alfa phase III trial, where the median OS in patients with 1 risk factor was 28.2 months vs. 16.3 months in those with 2 risk factors. ORR was 33.3% (95% CI: 25.9, 41.5) in patients with 1 risk factor and 31.7% (95% CI: 20.3, 45.0) in those with 2 risk factors. Median PFS in intermediate risk group patients with 1 or 2 risk factors was 10.7 months. 10

Given the high interest to examine the effect of lines of treatments on clinical outcomes by IMDC prognostic risk group, Analysis Group, Inc. (AGI) will conduct a study to further understand the clinical outcomes in mRCC patients treated with sunitinib as first-line stratified by IMDC prognostic risk groups in real-world clinical practices using the IMDC database. This will provide contemporary benchmarks for outcomes and survival among mRCC treated with first-line sunitinib in the real world. Additionally, the clinical heterogeneity within the IMDC intermediate risk group and impact of individual IMDC prognostic risk factors will be explored.

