7.3. Variables

Primary exposure

• Sunitinib as first-line therapy.

Outcomes

- OS, defined as the time between index date and death.
- TTD, defined as the time between index date and discontinuation of therapy due to any reason including progression, death, or toxicity.
- Reasons for treatment discontinuation, categorized as progression, death, toxicity, or other.
- Physician-assessed best response, defined as ORR (sum of partial response and complete response), progressive disease, and stable disease.

Covariates (assessed during the baseline period or at index date).

- Gender.
- Age at time of mRCC diagnosis.
- Race.
- Date of RCC diagnosis.
- Date of mRCC diagnosis.
- Prior nephrectomy.
- Date of nephrectomy (if applicable).
- Pathology.
 - Non clear cell RCC.
 - Clear cell RCC.
- Number of metastatic sites (eg., 1 site or more than 1 site).
- Site of metastases (eg, brain metastasis).
- IMDC prognostic risk factors.
 - Time from diagnosis to treatment initiation.
 - Karnofsky performance status at index date.
 - Serum hemoglobin at index date.

- Serum corrected calcium at index date.
- Neutrophil count (absolute count) at index date.
- Platelet count at index date.

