7.4. Data Sources

Data will be obtained retrospectively from the IMDC clinical sites.

The IMDC cohort is a multi-institutional cohort that collects data globally from 35 international cancer centers in the United States, Canada, Denmark, Greece, South Korea, Australia, New Zealand, Japan, Singapore, Italy, and Belgium. Demographic, clinical, laboratory, and outcome data on patients with mRCC are collected retrospectively from medical charts using uniform database templates and standardized definitions to ensure data are collected consistently. Medical records include longitudinal information on patient demographic and disease characteristics, oncology-specific workups and evaluations, treatment types and duration, concurrent diagnoses as documented in physician notes, and treatment discontinuation/halt decisions.

AGI will collaborate with [name] from the PPD who will serve as the principal investigator for this study and who is also the Chair of the IMDC, to obtain data from clinical centers. The clinical centers send data to the IMDC database, which is updated frequently (ie, quarterly or continuously). Data cleaning and consolidation of the data occur twice a year.

For this proposed study, a "limited" dataset of first-line sunitinib patients will be provided. The "limited" dataset will be anonymized and will not contain any personal data. All first-line sunitinib patients are included in the "limited" dataset, but only a select number of variables necessary to fulfill the study objectives will be included.

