7.7. Data Analysis

Identification of the Study Cohort

The study population of interest in the current study are patients treated with first-line sunitinib. Each patient's eligibility for study will be verified against the eligibility criteria.

Description of patient demographic and clinical characteristics among patients in the study cohort, stratified by IMDC prognostic risk group

Baseline demographic and clinical characteristics prior to the index date will be described using the mean (standard deviation [SD]) and median values for continuous variables and frequency distributions for categorical variables. Demographic and clinical characteristics will also be summarized, stratified by IMDC prognostic risk groups (ie, favorable, intermediate, and poor). Comparisons will be performed using chi-square tests or Fisher's exact test, as appropriate, for categorical variables and Wilcoxon-Mann-Whitney non-parametric tests for continuous variables.

Characterization of clinical outcomes of mRCC patients treated with first-line sunitinib

The following clinical outcomes will be stratified by IMDC prognostic risk groups (ie, favorable, intermediate, and poor) and KPS (eg, 0-40%, 50-70%, and 80-100%).

- OS and TTD will be analyzed using Kaplan-Meier estimator.
- Reasons for first-line sunitinib therapy discontinuation will be described using relative frequencies.
- Physician-assessed best tumor response (ie, objective response rate, stable disease, and progressive disease) to first-line sunitinib will be described using relative frequencies.

Indirect qualitative evaluation of the real-world clinical outcomes of mRCC patients treated with first-line sunitinib with that of phase II and III clinical trials

An indirect qualitative, side-by-side evaluation of clinical outcomes will be conducted between the following groups:

• Previously untreated sunitinib patients with intermediate or poor IMDC risk score from the real-world IMDC database *vs* previously untreated sunitinib patients with intermediate or poor IMDC risk score from the 1) CABOSUN trial, 2) CheckMate 214, and 3) sunitinib vs. IFN-α trial.

Subgroup analysis describing demographic and clinical characteristics and characterizing clinical outcomes among patients in the IMDC intermediate risk group, stratified by patients having only 1 vs 2 risk factors

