7.8. Limitations of the Research Methods

With an analysis of non-randomized treatment groups, unmeasured confounders and reporting bias could account for any observed associations. In addition, there may be potential biases in the retrospective study design (eg, selection bias, recall bias, and non-random missing data).

In addition, assessments of disease progression and tumor response in real-world settings may be based on heterogeneous criteria and assessment schedules. In contrast to clinical trials with protocol-specified definitions of clinical events, assessments of progression and clinical response in retrospective studies of clinical practice may not be made consistently across subjects and across physician practices.

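### Does the side-by-side with the trial sunitinib arms in Section 7.7 let any-cause TTD be read as PFS?

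*Combined protocol and SAP*

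**What the plan says.** The comparison is introduced in Section 7.7 with the words "An indirect qualitative, side-by-side evaluation of clinical outcomes will be conducted between the following groups". The groups are intermediate- or poor-risk patients on first-line sunitinib in the IMDC database, and the same risk groups in the sunitinib arms of CABOSUN, CheckMate 214 and the sunitinib versus interferon alfa trial.

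For those arms Section 5 gives PFS. For CABOSUN the cabozantinib figure is "compared with 5.6 months (95% CI: 3.4, 8.1) for patients taking sunitinib". For the interferon trial, "When intermediate and poor IMDC risk groups were combined. the median PFS was 10.6 months". For CheckMate 214 the sunitinib median is 8.4 months.

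Section 7.3 lists no PFS. Its time-to-event outcomes are OS and "TTD, defined as the time between index date and discontinuation of therapy due to any reason including progression, death, or toxicity". It also lists "Reasons for treatment discontinuation, categorized as progression, death, toxicity, or other" and physician-assessed best response. Section 7.8 cautions about outcome assessment in practice: "In contrast to clinical trials with protocol-specified definitions of clinical events, assessments of progression and clinical response in retrospective studies" of routine care may be inconsistent across subjects and practices.

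**The concern.** Section 5 motivates the study partly by the differences in PFS between these trials, and Section 7.7 returns to the same three. A reader will look for a real-world counterpart to 5.6, 8.4 and 10.6 months, and TTD is the only time-to-event outcome apart from OS.

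The two endpoints differ. TTD counts a stop for toxicity or any other reason as an event, and it does not count progression while treatment continues. The warning in Section 7.8 concerns how progression and response are measured; it does not say that TTD and PFS are different quantities. Section 5 also promises that "This will provide contemporary benchmarks for outcomes and survival among mRCC treated with first-line sunitinib in the real world". If median TTD were printed beside trial median PFS without comment, a difference of definition would be mixed with any true difference between practice and trial.

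**Working it through.** **What the text supports.** Study outcomes set against what Section 5 quotes for the combined intermediate and poor-risk sunitinib arms:

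| Outcome | Defined in 7.3 | Quoted in Section 5 for the combined arms |
|---|---|---|
| OS | yes | none (only by 1 versus 2 risk factors) |
| TTD | yes | none |
| Reasons for stopping | yes | none |
| Best response | yes | none (ORR only by 1 versus 2 risk factors) |
| PFS | no | 5.6, 8.4 and 10.6 months |

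So the only outcome quoted for those arms has no study counterpart. The meaning of clinical outcomes in the comparison is nevertheless recoverable. The paragraph just before it in Section 7.7 lists the four study outcomes. The subgroup paragraph just after it twice spells the term out as OS, TTD and ORR. Objectives 2 and 3 in Section 6 use the same set. The ordinary reading is that the side-by-side covers OS, TTD and response. What is left unstated is the trial quantity, if any, that TTD is set against.

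**Size if TTD were read as PFS.** The plan states no figure to reproduce, so this is an illustration. Inputs: median PFS 8.4 months (Section 5, CheckMate 214). Two further inputs are assumed because the documents do not give them: q, the share of stops that are neither progression nor death, at 10%, 20% and 30%; and d, the time treatment continues past progression, at 0 to 3 months. Hazards are taken as constant.

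Let λ = ln 2 / 8.4 be the hazard of progression or death and μ the hazard of other stops.

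- No lag: q = μ/(λ+μ), so median TTD = 8.4 × (1 − q). This gives 7.56, 6.72 and 5.88 months.
- Fixed lag d, applied to deaths as well for simplicity: q = 1 − [λ/(λ+μ)]·exp(−μd), and the median t solves λ(t − d) + μt = ln 2.

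| Median TTD (months) | d = 0 | d = 1 | d = 2 | d = 3 |
|---|---|---|---|---|
| q = 10% | 7.56 | 8.53 | 9.51 | 10.48 |
| q = 20% | 6.72 | 7.66 | 8.61 | 9.56 |
| q = 30% | 5.88 | 6.79 | 7.71 | 8.64 |

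The extremes are 8.4 − 5.88 = 2.5 months shorter and 10.48 − 8.4 = 2.1 months longer. The sign changes at d = 0.86, 1.78 and 2.74 months for q = 10%, 20% and 30%.

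**Two limits on these figures.**

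- The endpoint difference would not account for the spread between trials within the range shown: moving from 10.6 to 5.6 with no lag needs q = 1 − 5.6/10.6 = 47%.
- Constant hazards fit the protocol's own data poorly. Mixing exponentials with the interferon trial's medians of 10.7 (intermediate) and 2.4 (poor) in proportion 55:9, the combined median solves (55/64)·2^(−t/10.7) + (9/64)·2^(−t/2.4) = 0.5. That gives t = 8.7 months, against the 10.6 stated.

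**The case for a change.** The case for a change is a reasonable one. Reading the neighbouring lists into the comparison brings TTD into it, and PFS is the only time-to-event figure the protocol quotes for those arms. Misreading is therefore foreseeable, and because the direction of the discrepancy is unknown, a reader could not correct for it. Two or three sentences would deal with this and would need no new data.

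Part of this stands: the comparator for TTD is unstated, and no sentence says that TTD is not PFS. Several things reduce its weight.

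- The any-cause definition of TTD is explicit, so TTD is not presented as PFS.
- Discontinuation reasons are reported by risk group, so readers will see how many stops were for something other than progression. That does not turn TTD into PFS, and it does not show treatment continued past progression.
- Figures quoted as background do not fix the comparator. Whether the trial reports give OS, response or treatment duration for these arms cannot be judged from the protocol, so a like-for-like comparison cannot be ruled out.
- The benchmark sentence in Section 5 follows the description of outcomes by risk group. It refers to the study's own results, which this point does not affect.

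Adding a real-world PFS would not be a cheap remedy. Section 7.4 describes records of "treatment types and duration, concurrent diagnoses as documented in physician notes, and treatment discontinuation/halt decisions" and does not show that progression dates are held. A further extract could involve up to 35 centers, with data collection planned to end in September 2018 and the report due in January 2019. Any such PFS would also carry the measurement problem described in Section 7.8.

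**Conclusion.** No change to the plan is needed. The gap is real but small: Section 7.7 does not say what TTD is compared with in the trial arms. A competent analyst would set OS against OS and response against response, and would either leave TTD out of the side-by-side or label it as a different endpoint from PFS. Nothing in the plan as written directs otherwise, and no rule in it produces a wrong result.

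The consequence is confined to the reading of a qualitative comparison that has no test and is not among the numbered objectives in Section 6. No cohort, estimate, test or objective would change. The illustrated discrepancy, from 2.5 months shorter to 2.1 months longer on a PFS of 8.4 months, depends on assumed values of q and d and on constant hazards. It shows that the two endpoints are not interchangeable; it does not show a bias of known size or direction in this study.

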7.2. Setting

7.2.1. Inclusion Criteria

1. Patients will be selected based on the eligibility criteria listed below. Participation in interventional trial for mRCC disease is allowed. Subjects will be selected irrespective of their survival status.

Patients must meet all of the following inclusion criteria to be eligible for inclusion in the study:

- Diagnosed with mRCC;
- Initiated treatment post mRCC diagnosis and received sunitinib as first-line therapy;
- Age 18 years or over at the time of mRCC diagnosis;
- Actively treated at an IMDC clinical center.

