7.2.2. Exclusion Criteria

- Initiated first-line sunitinib treatment before 2010;
- Had non-clear cell mRCC.

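### The side-by-side with the trial arms places no KPS or brain-metastasis limit on the registry patients, so part of any difference could reflect who was eligible; a trial-like sensitivity column would be a cheap improvement

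*Combined protocol and SAP*

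**What the plan says.** Section 7.7 (Data Analysis) plans a descriptive comparison with published trials: "An indirect qualitative, side-by-side evaluation of clinical outcomes will be conducted between the following groups". The registry side is "Previously untreated sunitinib patients with intermediate or poor IMDC risk score from the real-world IMDC database". The trial side is "previously untreated sunitinib patients with intermediate or poor IMDC risk score from the 1) CABOSUN trial, 2) CheckMate 214, and 3) sunitinib vs. IFN-α trial". No restriction, matching, weighting or sensitivity subset is attached to it.

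The registry cohort is defined in sections 7.2.1 and 7.2.2. Inclusion requires metastatic disease, first-line sunitinib, adult age and active treatment at a consortium center. The only two exclusions are "Initiated first-line sunitinib treatment before 2010" and "Had non-clear cell mRCC". Section 7.2.1 adds that "Participation in interventional trial for mRCC disease is allowed".

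Section 7.3 lists KPS at index among the IMDC risk factors and, as a separate covariate, "Site of metastases (eg, brain metastasis". Section 7.7 also plans to stratify outcomes by KPS, with example bands of 0-40%, 50-70% and 80-100%, but this is not carried into the trial comparison.

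Section 7.8 names selection bias as a general risk of retrospective designs. Its one contrast with trials concerns how progression and response are assessed, not who was enrolled.

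**The concern.** The two sides share the label intermediate or poor risk, but not the route by which patients entered. The trial patients passed entry criteria; the registry patients only had to be treated. If the trials turned away patients with low performance status or brain metastases, and such patients do worse, the registry column would show shorter survival and time on treatment even if sunitinib worked identically in comparable patients.

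The study is meant to supply real-world benchmarks (section 5), and this table puts those benchmarks next to trial results. Readers will interpret any gap. As planned, nothing in the table lets them separate a difference in eligibility from a difference in outcome among similar patients, although two of the variables needed to begin doing so are already in the variable list.

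**Working it through.** The plan gives no figure that depends on this point, and no power calculation (section 7.5), so there is nothing to reproduce. The check is a reading of the text followed by an illustration.

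**1. What the shared label aligns**

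| Feature | Registry side | Aligned with the trial arms? |
|---|---|---|
| Line of therapy | First line (7.2.1) | Yes |
| Histology | Non-clear cell excluded (7.2.2) | Yes; section 5 describes all three trials as clear cell |
| IMDC group | Intermediate or poor (7.7) | Yes, as a combined label |
| KPS | No limit (7.2.1, 7.2.2) | In part |
| Brain metastases | No limit (7.2.1, 7.2.2) | No |

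KPS is only partly aligned because it is one of six IMDC factors in section 7.3, and section 7.7 defines intermediate risk as any one or two of them. A patient can be intermediate risk with or without the KPS factor, and the factor count does not record how low the KPS is. Brain metastasis is not one of the six.

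**2. What the documents do not give**

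They do not state the three trials' entry limits. They also do not give the share of registry patients outside such limits, or how those patients fare. All three are assumptions below.

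**3. Illustration**

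Inputs:
- *m*, the median in trial-like patients: 8.4 months, the CheckMate 214 sunitinib PFS median in intermediate/poor risk (section 5).
- *q*, the share of registry patients outside the trial limits: assumed 10-30%.
- *h*, their hazard ratio against the rest: assumed 1.5-2.5.

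With exponential survival in each part, the median *t* of the unrestricted cohort solves

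(1 − q) · 2^(−t/m) + q · 2^(−h·t/m) = 0.5

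| q | h | Left-hand side at t | t (months) | Change from 8.4 |
|---|---|---|---|---|
| 10% | 1.5 | 0.463 + 0.037 = 0.500 | 8.05 | −0.35 (−4%) |
| 20% | 2.0 | 0.439 + 0.060 ≈ 0.500 | 7.26 | −1.14 (−14%) |
| 30% | 2.5 | 0.418 + 0.082 = 0.500 | 6.26 | −2.14 (−25%) |

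The percentage change does not depend on *m*: from 10.6 months the same cases give 10.16, 9.16 and 7.90. With q = 0 or h = 1 there is no shift.

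The base is PFS, because that is the combined intermediate/poor outcome quoted for all three trials in section 5. The registry outcomes in section 7.3 are OS, TTD, reasons for discontinuation and best response. The table therefore shows direction and rough size under assumptions; it does not predict any planned result.

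**The case against.** The case on the other side has real weight.

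- **The plan claims little.** The comparison is labelled indirect and qualitative, has no test or effect estimate, and is not among the section 6 objectives. For a real-world benchmark the unrestricted cohort is the right population. This stands, and is why that column should stay. But the label only disclaims formal inference; it does not tell a reader how much of a gap comes from patients a trial might not have enrolled.
- **KPS is partly handled.** It enters the IMDC score, and KPS-stratified outcomes are planned, including an 80-100% band. This also stands in part. The strata are not specified within the intermediate/poor group, are not combined with brain status, and are not placed beside the trials.
- **Trial participants may be in the registry.** Section 7.2.1 allows it, which would dilute any gap. The documents do not say how many there are.
- **The remedy is incomplete.** Other entry criteria, such as organ function, are not in the variable list, so a restricted column could suggest more comparability than it has. That is answered by saying so beside the column.

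Two stronger readings are tempting and should not be drawn.

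First, a reader might infer from section 5 that matching on IMDC group has already been shown to fail, because sunitinib PFS in intermediate/poor patients was 5.6, 8.4 and 10.6 months across the three trials; the section itself remarks, "Based on the differences in PFS between these studies, patient IMDC prognostic risk group may play a role". But all three figures come from trial arms, which on the assumption used here all had entry limits. A spread among them says nothing about registry patients without such limits. Sampling error is also large: the 5.6 comes from 78 patients with a 95% CI of 3.4-8.1, which overlaps the CheckMate 214 interval (7.0-10.8) and meets the lower end of the third (8.1-10.9).

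Second, a reader might rule out risk mix as the cause of that spread. Mixing the section 5 medians for intermediate (10.7) and poor (2.4) risk exponentially, a 5.6-month median needs about 39% poor risk, against 9/(55 + 9) = 14% in the interferon trial and 21% in CheckMate 214. This fails. The documents give no risk mix for CABOSUN. At 21% poor the model gives 7.7 months, inside the CABOSUN interval. At 14% it gives 8.7 months, against the 10.6 reported in the trial that supplied its inputs.

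**Conclusion.** The gap is real and modest. The registry side has no KPS or brain-metastasis limit, no trial-like subset is planned for the side-by-side, and the variables for a partial one are already listed. Part of any registry-trial difference could therefore reflect who was eligible.

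This rests on the assumption that the trials limited performance status and brain metastases, which must be checked against their publications. The size cannot be derived from the documents. The illustrated shift of 4% to 25% depends wholly on the assumed shares and hazard ratios, and on a PFS base that the registry does not report. Its low end is negligible; its middle and upper cases could change how the table reads.

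It does not follow that the registry will look worse than the trials. The three trial medians themselves run from 5.6 to 10.6 months, trial participants may be in the registry, and the excluded share may be small. Nor does the point affect the study's main descriptive objectives.

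**What to change.** In section 7.7, keep the unrestricted intermediate/poor column as the real-world benchmark. For each of the three trials, add a sensitivity column limited to intermediate/poor registry patients who meet that trial's published performance-status and brain-metastasis limits, applied through KPS at index and site of metastases. If a trial had no such limit, its column is unchanged; if it used another performance-status scale, state the conversion.

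For each column report:
- the number removed by each limit;
- the number with unknown KPS or unknown brain status;
- the shift in OS, TTD and best response from the unrestricted column.

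State there, and in section 7.8, that the match is partial because other entry criteria, such as organ function, are not in the variable list.

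The cost is about one paragraph, up to three extra columns and a look-up of the trials' entry criteria; no new registry variables are needed. The restricted columns will have fewer patients and will lose those with unknown KPS or brain status. Section 7.5 puts first-line sunitinib patients at about 2,000-3,000 before exclusions, so a subset is plausibly large enough to describe, though the documents do not give its size.
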